6.3.2 End of Study/Study Completion Definition and Planned Reporting

No additional data will be collected, and the final analyses for the clinical study report will be conducted, after all patients enrolled in the study have discontinued from the trial either because modakafusp alfa is discontinued or because patients remaining on treatment have been transferred to an open-label rollover study, a single-patient investigational new drug (IND), or any other regulated form to access an investigational drug (Section 6.3.5).

6.3.3 Timeframes for Primary and Secondary Endpoints to Support Disclosures

Refer to Table 6.a for disclosures information for all primary and secondary endpoints.

Table 6.a Primary and Secondary Endpoints for Disclosure

Endpoint	Phase	Definition	Maximum Time Frame
Primary:			
Frequency and severity of TEAEs.	Phase 1b and phase 2 safety lead-in	Standard safety assessments.	Up to ~55 months.
Number of patients with DLTs.	Phase 1b and phase 2 safety lead-in	Standard safety assessments.	Up to ~55 months.
Number/percentage of patients with 1 or more SAEs.	Phase 1b and phase 2 safety lead-in	Standard safety assessments.	Up to ~55 months.
Number/percentage of patients with 1 or more TEAE leading to dose modifications and/or treatment discontinuation.	Phase 2 expansion	Standard safety assessments.	Up to ~55 months.
Secondary:			
MTD or PAD, if available.	Phase 1b	See Section 6.1.1.	During phase 1b.
RP2D.	Phase 1b and phase 2 safety lead-in	See Section 6.1.1	During phase 1b and phase 2 safety lead-in.
Frequency and severity of TEAEs according to the NCI CTCAE v5.0.	Phase 2 expansion	Standard safety assessments.	Up to ~55 months.
Number/percentage of patients with 1 or more SAEs.	Phase 2 expansion	Standard safety assessments.	Up to ~55 months.
Number/percentage of patients with 1 or more TEAE leading to dose modification and/or treatment discontinuation.	Phase 2 expansion	Standard safety assessments.	Up to ~55 months.
PK: C_{max} , t_{max} , AUC_t , AUC_{∞} , $t_{1/2z}$, CL, and V_{ss}	Phase 2 safety-lead in	Standard PK assessments	Dose escalation phase: C1D1-C1D4, C2D1-C2D4, and Day 1 of Cycles 3-6. Safety Lead-in phase: C1D1-C1D15, C3D1-C3D15, and Day 1 of Cycle 2/ Cycle 4-beyond.
ORR per RECIST v1.1.	Phase 1b	The proportion of patients who achieve CR or PR (determined by the investigator) during the study in response-evaluable population.	Up to ~55 months.
PFS per RECIST v1.1 for patients with solid tumors.	Phase 1b and phase 2	The time from the date of the first dose of study	Up to ~55 months.

Table 6.a Primary and Secondary Endpoints for Disclosure

Endpoint	Phase	Definition	Maximum Time Frame
		drug to the date of first documentation of PD according to RECIST v1.1 or death due to any cause, whichever occurs first.	
OS	Phase 1b and phase 2	The time from the date of first dose of study drug to the date of death due to any cause.	Up to ~55 months.
DCR	Phase 1b and phase 2	CR + PR + SD	Up to ~55 months.
DOR	Phase 1b and phase 2	The time from the date of first documentation of a PR or better to the date of first documentation of PD for responders (PR or better).	Up to ~55 months.
TTP	Phase 1b and phase 2	The time from the date of the date of the first dose of study drug to the date of first documentation of PD according to RECIST v1.1.	Up to ~55 months.
ORR, DCR, DOR, TTP, and PFS based on iRECIST.	Phase 2 expansion	See above.	Up to ~55 months.
Modakafusp alfa–induced Type I IFN gene expression signature in peripheral blood.	Phase 1b and phase 2	See Section 13.6.	Up to ~55 months.
Anti-modakafusp alfa antibody incidence and titer.	Phase 1b and phase 2	See Section 13.6.	Up to ~55 months.

AUC_t: area under the plasma concentration versus time curve from 0 to time t; CxDx: Cycle x Day x; CL: clearance; C_{max}: maximum observed concentration; CR: complete response; DCR: disease control rate; DOR: duration of response; DLT: dose-limiting toxicity; IFN: interferon; RECIST v1.1: Response Evaluation Criteria in Solid Tumors, Version 1.1; ORR: overall response rate; OS: overall survival; PFS: progression-free survival; PK: pharmacokinetic(s); PR: partial response; RO: receptor occupancy; SAE: serious adverse event; SD: stable disease; t_{1/2z}: terminal disposition phase half-life; TEAE: treatment-emergent adverse event; t_{max}: time of first occurrence of C_{max}.

6.3.4 Total Study Duration

The estimated time frame for study completion is 55 months (12 months of enrollment in escalation, 18 months of enrollment in expansion, 24 months of treatment, and 1 month of follow-up).

6.3.5 Posttrial Access

At the end or termination of the study (Section 9.4), ongoing patients may continue to receive modakafusp alfa as a SA or in combination with pembrolizumab in an extension phase of this study or will be given the opportunity to enroll in a separate open-label rollover study, a single-patient IND, or other regulated access to continue receiving modakafusp alfa as a SA or in combination with pembrolizumab if, in the opinion of the investigator and confirmed by the sponsor, they have experienced a clinically important benefit from modakafusp alfa or in combination with pembrolizumab received in the study, have no alternative therapeutic option, and would be harmed without continued access. Patients may receive modakafusp alfa as a SA for up to 1 year or in combination with pembrolizumab for up to 2 years.

6.3.5.1 Duration of Posttrial Access

Continued access to modakafusp alfa will be terminated for individuals who are no longer benefitting from modakafusp alfa (eg, they have completed the recommended course of therapy or their disease has resolved), the benefit-risk no longer favors the individual, if modakafusp alfa becomes available either commercially or via another access mechanism, or when an alternative appropriate therapy becomes available. Posttrial access may be terminated in a country or geographical region where marketing authorization has been rejected, the development of modakafusp alfa has been suspended or stopped by the sponsor, or modakafusp alfa can no longer be supplied.

7.0 STUDY POPULATION

7.1 Inclusion Criteria

Each patient must meet all the following inclusion criteria to be enrolled in the study:

1. Adult patients aged ≥ 18 years.
2. Eastern Cooperative Oncology Group (ECOG) performance status of 0-1.
3. Life expectancy >12 weeks according to investigator's judgment.
4. Phase 1b dose escalation: Eligible patients must have histologically confirmed advanced (locoregionally recurrent, not amenable to curative therapy) or metastatic solid tumors.
5. Measurable disease per RECIST v1.1. At least 1 target lesion amenable for biopsy is required for enrollment in phase 1b. A minimum of 1 target lesion for response assessment is required for enrollment in phase 2. A separate lesion amenable for biopsy is required for enrollment in phase 2 for cohorts I and II post futility analysis and for all patients (safety lead-in and expansion) with subgroup III melanoma.
6. Phase 1b Dose Escalation: Patients with histologically confirmed advanced locally (locoregionally recurrent, not amenable to curative therapy) or metastatic solid tumors.

Phase 2 Dose Expansion:

The combination cohorts, including patients in the safety-lead phase, will enroll patients with unresectable/metastatic melanoma in the following subgroups:

- I. Unresectable/metastatic histologically confirmed cutaneous melanoma with primary resistance to no more than 2 prior lines of anti-PD1 containing treatments in the metastatic setting.
 - II. Unresectable/metastatic histologically confirmed cutaneous melanoma with acquired resistance to no more than 2 prior lines of anti-PD1 containing treatments in the metastatic setting.
 - III. Unresectable/metastatic histologically confirmed cutaneous melanoma naive to prior anti-PD1 containing treatments in the metastatic setting.
- Patients with BRAF V600E mutant melanoma may have received prior BRAF inhibitor therapy.
 - For cohorts I and II, there is no limitation of total number of prior line(s) of therapy, but the number of prior line(s) containing anti-PD1 must be ≤ 2 in the metastatic setting.
 - For the expansion cohort III, patients who received an anti-PD-1 treatment in the adjuvant setting must have completed that treatment at least 6 months prior to enrollment and must not have progressed on the anti-PD1 adjuvant treatment.
 - Primary resistance is defined as a best response of PD or SD < 6 months to an anti-PD1 alone or in combination with other agents (ie, CTLA4) in the initial anti-PD1 containing treatment.
 - Acquired resistance is defined as a progression following a best response of CR, PR, or SD > 6 months to a prior anti-PD1 alone or in combination with other agents (ie, CTLA4).
7. Reproductively female patients who:
- Are postmenopausal for at least 2 years before the screening visit, OR
 - Are surgically sterile, OR
 - If they are of childbearing potential (as defined in Section 9.3.9), due to unknown risks and potential harm to an unborn child/infant, must agree to the following:
 - Agree to practice 1 highly effective method of contraception (Section 8.9.1) and 1 additional effective (barrier) method at the same time, from the time of signing the informed consent through 7 days after the last dose of modakafusp alfa or 4 months after the last dose of pembrolizumab, whichever is longer, OR
 - Agree to practice true abstinence, when this is in line with the preferred and usual lifestyle of the subject. (Periodic abstinence [eg, calendar, ovulation, symptothermal, postovulation methods], withdrawal, spermicides only, and lactational amenorrhea are not acceptable methods of contraception. Female and male condoms should not be used together.)

- Agree not to donate an egg or eggs (ova) or breastfeed a baby during the study and through 7 days after the last dose of modakafusp alfa or 4 months after the last dose of pembrolizumab, whichever is longer.
8. Reproductively male patients, even if surgically sterilized (ie, status postvasectomy), who:
 - Agree to practice effective barrier contraception (Section 8.9.1) during the entire study treatment period and through 7 days after the last dose of modakafusp alfa (no restriction for pembrolizumab), OR
 - Agree to practice true abstinence, when this is in line with the preferred and usual lifestyle of the subject. (Periodic abstinence [eg, calendar, ovulation, symptothermal, postovulation methods], withdrawal, spermicides only, and lactational amenorrhea are not acceptable methods of contraception. Female and male condoms should not be used together.)
 - Agree not to donate sperm during the study and through 7 days after the last dose of modakafusp alfa (no restriction for pembrolizumab).
 9. Voluntary written consent must be given before performance of any study-related procedure not part of standard medical care, with the understanding that consent may be withdrawn by the patient at any time without prejudice to future medical care.
 10. Adequate bone marrow reserve and renal and hepatic function based on the following laboratory parameters:
 - Absolute neutrophil count (ANC) $\geq 1.0 \times 10^9/L$, platelet count $\geq 75.0 \times 10^9/L$, and hemoglobin ≥ 80 g/L without growth factor or transfusion support for ANC and platelets in the preceding 2 weeks.
 - Total bilirubin ≤ 1.5 times the upper limit of normal (ULN).
 - Serum alanine aminotransferase or aspartate aminotransferase ≤ 3.0 times the ULN (< 5 times the ULN if liver enzyme elevations are due to liver metastases).
 - Creatinine < 1.5 times the ULN or estimated glomerular filtration rate (eGFR) ≥ 30 mL/min/1.73 m² using the Modification of Diet in Renal Disease (MDRD) (Levey et al. 2006) or Chronic Kidney Disease Epidemiology Collaboration (CKD-EPI) (Levey et al. 2009) equations.
 11. Patients must agree to the applicable biopsy requirements as detailed in the SOE.

7.2 Exclusion Criteria

Patients meeting any of the following exclusion criteria are not to be enrolled in the study:

1. Treatment with any SoC or investigational anticancer drug within 28 days or 5 half-lives before administration of modakafusp alfa, whichever comes first. The washout period is 3 weeks for previous major surgery, 2 weeks for previous radical radiation (including chemoradiation and whole-brain radiation), and 5 days from last dose for focal radiation for symptomatic metastases.

2. Persistent toxicity from previous treatments that has not resolved to \leq CTCAE v.5 Grade 1 prior to administration of modakafusp alfa, except for alopecia, Grade 2 neuropathy, Grade 2 asthenia/fatigue, or autoimmune endocrinopathies with stable replacement therapy.
3. History of any of the following \leq 6 months before the first dose of modakafusp alfa: New York Heart Association Grade III or IV congestive heart failure, unstable angina, myocardial infarction, unstable symptomatic ischemic heart disease, any ongoing symptomatic cardiac arrhythmias Grade >2 , pulmonary embolism, symptomatic cerebrovascular events, or any other serious cardiac condition (eg, symptomatic pericardial effusion or restrictive cardiomyopathy). Chronic, stable atrial fibrillation on stable anticoagulant therapy, including low molecular-weight heparin, is allowed.
4. Baseline QTcF >480 msec (Grade ≥ 2), history of congenital long QT syndrome, or torsades de pointes.
5. History of immune-related AEs related to treatment with prior anti-PD1/PD-L1 that required treatment discontinuation (phase 2).
6. Psychiatric illness/social circumstances that would limit compliance with study requirements and substantially increase the risk of AEs or has compromised ability to provide written informed consent.
7. History of uncontrolled brain metastasis or previously treated metastases receiving corticosteroid dose ≥ 20 mg/day of prednisone equivalent at the time of receiving the first dose of modakafusp alfa.
Note: Patients with carcinomatous meningitis or leptomeningeal disease are excluded, regardless of clinical stability.
8. Patients with uveal (ocular) or mucosal melanoma (phase 2).
9. Patients with acral lentiginous melanoma are excluded in phase 2 except for the safety lead-in phase.
10. Ongoing or active infection.
11. Known history of HIV infection or any other relevant congenital or acquired immunodeficiency.
12. Known hepatitis B (HBV) surface antigen seropositive or detectable hepatitis C infection viral load. *Note:* Patients with a positive HBV core antibody can be enrolled but must have an undetectable hepatitis B viral load.
13. Autoimmune disease requiring systemic immunosuppressive therapy. Patients with immune mediated endocrine deficiency from previous therapy with stable hormone replacement are exceptions.
14. History of severe allergic or anaphylactic reaction to recombinant proteins or excipients used in modakafusp alfa or pembrolizumab formulation.

15. Patients who are lactating and/or breastfeeding or have a positive urine or serum pregnancy test during the screening period.

8.0 STUDY DRUG

8.1 Study Drug Administration

All protocol-specific criteria for administration of study drug must be met and documented before drug administration. Study drug will be administered only to eligible patients under the supervision of the investigator or identified subinvestigator(s).

The initial dose should be based on a patient's weight at screening and only adjusted if there is a $\geq 10\%$ change in body weight.

Investigational sites should refer to the pharmacy manual for preparation of each dose. Modakafusp alfa doses < 1.5 mg/kg will be administered over 1 hour (± 10 minutes). Modakafusp alfa doses ≥ 1.5 mg/kg will be administered over 2 hours (± 10 minutes) and could be extended to 4 hours at the investigator's discretion. Any decrease in infusion duration must be discussed with and agreed upon by the sponsor. If a patient presents with an infusion-related reaction at any dose level, the duration of the infusion may be extended per investigator's discretion. Total time from modakafusp alfa dosing solution preparation until end of infusion must not exceed 7 hours.

In the combination treatment cohorts, the recommended pembrolizumab dose of 400 mg will be administered as an IV infusion over 30 ± 10 minutes Q6W in combination with modakafusp alfa. Please see premedication and observation guidelines in Section 8.8.1.

Pembrolizumab will be administered before modakafusp alfa on days when both modakafusp alfa and pembrolizumab are given. At least 30 minutes should elapse between the completion of the infusion of the first study drug and the initiation of the infusion of the second study drug.

8.2 Definitions of Dose-Limiting Toxicities

Toxicity will be evaluated according to the NCI CTCAE v 5. A DLT is defined as any of the following AEs that occur in the escalation phase or in the combination safety lead-in phase during Cycle 1 unless they are considered by the investigator to be clearly unrelated to therapy with modakafusp alfa.

- Any Grade 5 TEAE.
- Febrile neutropenia: Grade ≥ 3 neutropenia ($ANC < 1.0 \times 10^9/L$) with fever and/or infection, where fever is defined as a single temperature $> 38.3^\circ C$ or sustained temperature of $\geq 38^\circ C$ for more than 1 hour.
- Grade 4 neutropenia lasting > 7 days.
- Grade 4 thrombocytopenia lasting more than 7 consecutive days, or if platelet transfusion is required, or if Grade ≥ 2 bleeding happens at any moment. A platelet count $< 10 \times 10^9/L$ at any time is a DLT.

- Grade ≥ 3 thrombocytopenia lasting longer than 14 days or accompanied by Grade ≥ 2 bleeding.
- **Any Grade 3 immune-related AEs such as pericarditis, pneumonitis, cardiotoxicity, hepatitis, or neurotoxicity.**
- Delay in the initiation of Cycle 2 by more than 14 days from the calculated start date due to a lack of adequate recovery of treatment-related hematological or nonhematologic toxicities.
- Any Grade ≥ 3 nonhematologic toxicity **with the following exceptions:**
 - Grade 3 arthralgia/myalgia that responds to nonsteroidal anti-inflammatory drugs (NSAIDs) within 1 week.
 - Grade 3 fatigue that lasts < 3 days.
 - Grade 3 endocrine disorder that is managed with or without therapy and the patient is asymptomatic.
 - Grade 3 or 4 inflammatory reaction attributed to a local antitumor response.
 - Grade 3 or 4 asymptomatic laboratory changes (other than renal and hepatic laboratory values) that can be successfully corrected (reversion of Grade 4 events to Grade ≤ 2 , reversion of Grade 3 events to Grade ≤ 1 or baseline) within 72 hours.
 - Isolated Grade 3 elevation of ALT and/or AST that resolves to Grade ≤ 1 or baseline within 7 days.
 - Grade 3 nausea and/or emesis that can be controlled to Grade < 3 in ≤ 3 days with the use of optimal antiemetics (defined as an antiemetic regimen that employs both a 5-hydroxytryptamine 3 serotonin receptor antagonist and a corticosteroid given in standard doses and according to standard schedules).
 - Grade 3 rash and pruritis that respond to a standard treatment and resolve or improve to Grade < 3 within 7 days.
 - Grade 3 diarrhea that can be controlled to Grade < 3 in ≤ 3 days with appropriate treatment.
 - Any other Grade 3 TEAE for which NCI CTCAE v5 Grade 4 or 5 does not exist or the NCI CTCAE does not consider the AE Grade 4 to be life-threatening.
- Any Grade 2 nonhematologic toxicity that is considered by the investigator to be related to study drug and dose-limiting.

In the dose escalation phase, DLTs are defined as events meeting the criteria above that occur before Cycle 2 Day 1 administration. TEAEs meeting DLT definitions occurring in later cycles or during expansion will determine the suitability of the MTD as the RP2D.

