4.3.5 Potential Overlapping Toxicities

Nonclinical toxicology studies evaluating the combination of modakafusp alfa and pembrolizumab were not conducted and are not warranted per ICH S9 ([ICH 2018](#)). Pembrolizumab is a mAb that binds to the human PD-1 receptor and blocks the interaction of PD-1 with PD-L1/PD-L2.

Modakafusp alfa and pembrolizumab both activate the immune system, so known PD-1 immunotherapy-related toxicities (eg, pneumonitis, colitis, hepatitis, dermatitis, IRRs, endocrinopathies, and nephritis) observed following the administration of pembrolizumab may be enhanced when combined with modakafusp alfa. Details regarding the full safety profile of pembrolizumab can be found in the FDA-approved package insert ([Keytruda \(pembrolizumab\) PI 2018](#)). To minimize the risk to patients treated with modakafusp alfa and pembrolizumab, phase 2 will include a safety lead-in phase for the combination cohorts to determine the safety and tolerability of the combination doses and regimen. Pembrolizumab will be administered at the approved dose and schedule of 400 mg IV once every 6 weeks (Q6W) to maximize the possibility of observing clinical benefit.

The safety of the pembrolizumab and pegylated interferon alfa-2b (PEG-IFN) combination was studied in 2 phase 1/2 studies. Seventeen patients were enrolled in the Keynote-029 trial ([Atkins et al. 2018](#)), 5 with melanoma and 9 with renal cell carcinoma (RCC). Across dose levels, the most common treatment-related AEs of any grade were fatigue (n = 11, 65%), pyrexia (n = 7, 41%), chills, diarrhea and nausea (n = 6, 35% each). Grade 3 to 4 AEs were fatigue (n = 1), AST increase (n = 1), neutropenia (n = 1), and depression (n = 2). Forty-three patients with melanoma were enrolled in the Keynote-020 trial ([Davar et al. 2018](#)). The most frequent treatment-related toxicities were Grade 1 hyponatremia (11.1%), Grade 2 lymphopenia (10.8%), Grade 3 hyponatremia (10.3%), Grade 3 lymphopenia (12%) and Grade 3 fatigue (16.2%). Fifteen patients (34.9%) developed immune-related AEs (irAE) of any grade, including vitiligo (16.3%), hypothyroidism (16.3%), and one patient each with adrenal insufficiency (Grade 3), pneumonitis (Grade 4), and uveitis (Grade 4). No treatment-related deaths occurred.

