8.4 Phase 2 Modakafusp Alfa Dose Expansion

A minimum of 3 patients will be enrolled at the modakafusp alfa RP2D in combination with pembrolizumab 400 mg Q6W to evaluate safety and tolerability in a single safety lead-in phase. The safety lead-in phase will start with the enrollment of 3 initial patients to evaluate the tolerability during the Cycle 1 DLT evaluation period of modakafusp alfa with pembrolizumab. If there are no DLTs in the first 3 patients during Cycle 1 of the safety lead-in period with modakafusp alfa SA RP2D in combination with pembrolizumab 400 mg Q6W, the combination dose and regimen could be selected for the 3 melanoma disease cohorts.

If there is 1 DLT in the initial 3 patients in the safety-lead in period, an additional 3 patients will be enrolled at the same modakafusp alfa RP2D in combination with pembrolizumab 400 mg Q6W. If there are ≥ 2 DLTs in the first 3 patients at the modakafusp alfa SA RP2D, enrollment will resume at the next lower dose level of modakafusp alfa RP2D in combination with pembrolizumab. Other approved pembrolizumab dosing regimens (ie, 200 mg Q3W) could be tested in the safety-lead in period if 400 mg Q6W in combination with modakafusp alfa at one dose lower than RP2D is intolerable. For the safety lead-in period, patient enrollment will be staggered between the first and second patients by 7 days in the first dose cohort. The second and third patients can be dosed concurrently if the first patient in the cohort has gone through the Day 8 visit without clinically significant acute toxicities. Subsequent cohorts, if any, will not require staggering between patients.

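### The DLT attribution clause for the combination lead-in names only modakafusp alfa, so an event clearly due to pembrolizumab alone drops out of the count used to judge the two-drug regimen

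*Protocol*

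**What the plan says.** Protocol section 8.2 defines a DLT once, for listed events that "occur in the escalation phase or in the combination safety lead-in phase during Cycle 1", and then exempts them "unless they are considered by the investigator to be clearly unrelated to therapy with modakafusp alfa". The list that follows includes "Any Grade 3 immune-related AEs such as pericarditis, pneumonitis, cardiotoxicity, hepatitis, or neurotoxicity" and, with exceptions, any Grade 3 or higher nonhematologic toxicity.

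Two items in the same list use other attribution terms. The Cycle 2 delay criterion speaks of treatment-related toxicity. The Grade 2 nonhematologic criterion requires an event "considered by the investigator to be related to study drug and dose-limiting".

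Section 8.4 describes the lead-in as starting with three patients "to evaluate the tolerability during the Cycle 1 DLT evaluation period of modakafusp alfa with pembrolizumab". With no DLT in three, the dose and regimen may be selected. With one, three more patients are enrolled at the same dose. With two or more, enrollment resumes at the next lower modakafusp alfa level. Other approved pembrolizumab regimens "could be tested in the safety-lead in period if 400 mg Q6W in combination with modakafusp alfa" at one dose level below the RP2D is intolerable.

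Section 4.3.5 says the lead-in is there "to determine the safety and tolerability of the combination doses and regimen", and that known PD-1 toxicities "may be enhanced when combined with modakafusp alfa". Section 5.2.1 makes the number of patients with DLTs a primary endpoint for the lead-in. SAP section 7.3 builds the lead-in part of the DLT-evaluable set on having a DLT, but does not say to which agent relatedness applies.

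**The concern.** The regimen under test in the lead-in is two drugs, but the exemption asks about only one. Read literally, an investigator who is sure that modakafusp alfa played no part must leave the event out of the count, even if it was severe, occurred in Cycle 1 and was caused by the other half of the regimen.

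The DLT count is a primary lead-in endpoint and feeds the 0, 1, or 2-or-more rule that precedes three expansion cohorts of up to 25 patients each (3 × 25 = 75). With three patients, one reclassified event moves the result from one branch of that rule to another. The error goes one way: any event lost makes the combination look better tolerated.

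**Working it through.** There is no lead-in DLT rate, error rate or operating characteristic in either document, so there is no stated figure to reproduce. The operating characteristics in Protocol Appendix E and SAP Appendix C concern single-agent escalation. The check is first textual, then a labelled illustration.

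**Setting the sections side by side**

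1. Scope. Section 8.2 covers escalation and lead-in with one clause, and that clause names modakafusp alfa only. No other section of the protocol or SAP adds an attribution rule for the combination.
2. Purpose. Sections 4.3.5 and 8.4 both describe the lead-in as a judgement on the combination.
3. Consequence. Section 8.4 lets intolerability lead to a different pembrolizumab regimen, yet toxicity due to pembrolizumab alone is what the clause filters out of the DLT count.
4. Wording. Treatment-related and study drug, in the list itself, do not match the lead sentence. SAP section 7.8 treats both agents as study drugs when it describes exposure.
5. A case that meets the exemption. Section 8.1 gives pembrolizumab first, with at least 30 minutes before modakafusp alfa starts. A Grade 3 or higher reaction during the Cycle 1 Day 1 pembrolizumab infusion happens before any modakafusp alfa has been given, so it is clearly unrelated to that drug. Under SAP section 7.3, if that patient then fails to receive all Cycle 1 doses, the patient also falls outside the DLT-evaluable set, because no DLT was recorded.

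**Illustration of size (assumed inputs)**

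Let p be the true per-patient probability of a DLT-qualifying Cycle 1 event, and f the fraction of those events excluded because modakafusp alfa is clearly ruled out. Patients are taken as independent. The counted rate is q = p(1 − f), and for the first three patients:

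- P(0 of 3) = (1 − q)³
- P(1 of 3) = 3q(1 − q)²
- P(2 or more of 3) = 3q²(1 − q) + q³

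With p = 0.25:

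| f | q | P(0 of 3) | P(1 of 3) | P(2 or more of 3) |
|---|---|---|---|---|
| 0 | 0.250 | 0.750³ = 0.422 | 0.422 | 0.156 |
| 0.10 | 0.225 | 0.775³ = 0.465 | 0.405 | 0.129 |
| 0.40 | 0.150 | 0.850³ = 0.614 | 0.325 | 0.061 |

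To show dependence on p, hold f at 0.25:

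- p = 0.20 (q = 0.15): P(0 of 3) goes from 0.512 to 0.614, and P(2 or more of 3) from 0.104 to 0.061.
- p = 0.40 (q = 0.30): P(0 of 3) goes from 0.216 to 0.343, and P(2 or more of 3) from 0.352 to 0.216.

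The calculation stops at the first three patients because section 8.4 states no decision rule for the six-patient result.

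**The case against.** The strongest reply is that the clause is conservative and has a sensible design reason.

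- **The bar is high.** Only events clearly unrelated to modakafusp alfa are removed. Joint, possible or uncertain causes stay in. A reader might infer that any toxicity put down to pembrolizumab is ignored; the text does not say that. A reader might also infer that typical immune-related events would be lost. Section 4.3.5 says both drugs activate the immune system and may enhance such events, and section 8.2 lists Grade 3 immune-related events as DLTs, so ruling modakafusp alfa out would usually be hard. This stands, and it narrows the point considerably.
- **The count is not the only safeguard.** Section 5.2.1 also makes TEAEs, SAEs and TEAEs leading to dose modification or discontinuation primary for the lead-in, with no attribution filter, and SAP section 7.12.1 counts treatment-emergent events from the first dose of any study treatment. Section 6.1.2 places a review of safety data before expansion, and zero of three only permits selection. It would therefore be wrong to infer that the DLT count alone fixes the expansion regimen. This stands too, although that review has no stated criterion.
- **The response to DLTs is a lower modakafusp alfa level.** The pembrolizumab dose cannot be modified (section 8.6.3.2), so it may seem odd for an event modakafusp alfa did not cause to lower the modakafusp alfa dose. This is a real cost of any change. But neither document gives it as the reason for the clause, and it does not fit the section 8.4 provision under which the pembrolizumab regimen itself may change.

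**Conclusion.** The point holds in a limited form. The attribution clause in section 8.2 does not match the purpose that sections 4.3.5 and 8.4 give the lead-in, and it is out of step with two criteria in its own list. What is lost from the DLT count is confined to events due to pembrolizumab with modakafusp alfa clearly ruled out, most plainly a severe reaction during the first pembrolizumab infusion. Those events remain visible in the other safety endpoints.

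The size is unknown, because it depends on two quantities the documents do not give: the rate of qualifying events and the share excluded. At an assumed rate of 0.25 with 10% to 40% excluded, the chance of clearing at 0 of 3 rises by about 4 to 19 percentage points (0.465 − 0.422 = 0.043; 0.614 − 0.422 = 0.192), and the chance of 2 or more of 3 falls by about 3 to 10 points (0.156 − 0.129 = 0.027; 0.156 − 0.061 = 0.095). Given the high bar for exclusion, the lower end may be nearer the truth, but nothing in the documents settles that.

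**What to change.** Reconcile protocol section 8.2 (the lead sentence, the Cycle 2 delay criterion and the Grade 2 criterion), section 8.4 and the lead-in part of the DLT-evaluable set in SAP section 7.3 with the aim in section 4.3.5. The agent or agents to which relatedness applies in the lead-in should match the regimen whose tolerability the DLT count is used to judge, and one term should be used throughout. The wording for single-agent escalation can stay as it is. The exact clinical criterion is for the sponsor to set.

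The drafting cost is about one clause in section 8.2, plus matching terms elsewhere. The substantive cost should be stated openly: if pembrolizumab-attributed events count, the lead-in DLT count may be slightly higher, and some of those events could trigger the lower modakafusp alfa level under section 8.4.
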